4.3 Safety

- Incidence and severity of serious adverse events (SAEs) and adverse events (AEs)
- Frequency of change in clinically-significant vital signs, physical exam or neurological exam
- Plasma glucose level <70mg/dl
- Change in weight

5 Study Design

This study is a single center trial to determine dose finding, safety and tolerability of 3 doses of intranasal (IN) regular insulin (Table #2) and placebo in patients with Parkinson's disease.

Table 2: Intranasal Drug Dosing

Group	Drug	Dose	Volume	N=
Dose group 1	Insulin	20 IU/IN (10 IU, one nostril, twice daily)	100µl	7
Dose Group 2	Insulin	40 IU/IN (10 IU, each nostril, twice daily)	100µl	7
Dose Group 3	Insulin	80 IU/IN (20 IU, each nostril, twice daily)	200µl	9
Dose Group 4	Placebo	0.9% Saline (each nostril, twice daily)	200µl	7

After written informed consent has been obtained from the subject and family member/caregiver, subjects will be screened to assess study eligibility based on study inclusion/exclusion criteria. Subjects who are eligible at the end of the screening visit (Visit 1) will be scheduled for a baseline and randomization visit (Visit 2). During the baseline visit, subjects will be administered a cognitive battery. Subjects will also undergo a neurological examination, including the UPDRS (United Parkinson's Disease Rating Scale- MDS) to be performed in the "ON-STATE" (after taking Anti-Parkinson's medications according to the subject's regular medication schedule). A final safety/assessment visit will take place 3 weeks after visit 2 at which time the tests will be re-administered.

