6.1.2 Exclusion Criteria

A subject will not be included for consideration in this study if any of the following criteria are met:

1. Subject who has atypical Parkinson's syndrome(s) due to drugs (e.g., metoclopramide, neuroleptics), metabolic neurogenetic disorders (e.g., Wilson's Disease), encephalitis, cerebrovascular disease, or degenerative disease (e.g., progressive Supranuclear Palsy, Multiple system atrophy, corticobasal degeneration, Lewy Body dementia)
2. Subject has medical history and/or clinically determined disorders: chronic sinusitis, untreated thyroid disease, or significant head trauma.
3. Subject has history of any of the following: moderate to severe pulmonary disease, poorly controlled congestive heart failure, significant cardiovascular and/or cerebrovascular events within previous 6 months, condition known to affect absorption, distribution, metabolism, or excretion of drugs such as any hepatic, renal or gastrointestinal disease or any other clinically relevant abnormality that inclusion would pose a safety risk to the subject as determined by investigator.
4. Subject has had previous nasal and/or oto-pharyngeal surgery and severe deviated septum and/or other anomalies.
5. Subject has history of any psychiatric illness that would pose a safety risk to the subject as determined by investigator.
6. Subject is currently taking sedative medications that are clinically contraindicated as determined by investigator.
7. Subject has undergone a recent change (<1 month) in their anti-parkinsonian medication, cholinesterase inhibitor or anti-depressant medication.
8. Subject has current or recent drug or alcohol abuse or dependence as defined by DSM-IV TR.
9. Screening laboratory results that are medically relevant, in which inclusion would pose a safety risk to the subject as determined by investigator.
10. The subject has participated in a clinical trial investigation within 3 months of this study.
11. The subject has an insulin allergy.
12. The subject has Insulin-dependent diabetes

7 Study Assessments and Procedures

A summary of study events and procedures is outlined in the Study Visit Table. Demographic, Screening, and Baseline Assessments are described in Sections 7.1.1-7.1.2, the Treatment Phase is outlined in Sections 7.1.2-7.1.5, and the Safety monitoring are detailed in Section 7.3; details of neuropsychological assessments are outlined in Section 7.5.

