7.1 Demographic and Baseline Assessments

7.1.1 Visit 1: Screening

The following procedures will be performed at this visit:

- Obtain written informed consent from study partner and subject (or subject's legally authorized representative) prior to any study related procedures.
- Administer MoCA

- Review Inclusion/Exclusion Criteria.
- Review medical history, as it pertains to inclusion/exclusion criteria, such as research diagnosis, disease severity, and course of PD
- Obtain subject's demographic information (date of birth, gender, race, education, etc.).
- Obtain details of medications taken over the course of the last 30 days
- Complete physical exam, including neurological exam with UPDRS part III. Collect vital signs, height and weight prior to ECG and blood draw.
- Obtain laboratory studies
- Perform a standard 12-lead ECG.
- Study Drug administration training, including Study Drug Diary Training
- Hypoglycemia rescue training
- Visit 2 will be scheduled within 2 weeks (\pm 5 days).

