7.1.2 Visit 2: Baseline/Initial Treatment Visit (Week 0)-fasting

The following procedures will be performed at this visit:

- Review Inclusion/Exclusion Criteria.
- Collect vital signs, orthostatic vital signs and weight.
- Collect concomitant medication information and record AEs/SAEs.
- Neuropsychological testing, including scales for mood, apathy and suicidality assessment (7.5)
- Perform UPDRS III
- Obtain laboratory studies, blood draw and glucose finger sticks
- Study Drug administration training (following cognitive testing).
- Hypoglycemia rescue training.
- Randomization of subject
- Administer first intranasal dose in clinic and provide study kit
- Visit 3 will be scheduled in 21 days (\pm 5 days).

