12.1 Statistical Analysis Overview

Due to the small sample size of this study, statistical analysis will be mainly exploratory and descriptive: t-tests (or Mann-Whitney u-tests if normality of the data is not met) are used to compare the difference of a continuous measure between groups (such as patient age at baseline, various efficacy measures), and contingency tables and chi-square tests are used to compare the difference of a categorical variable (such as patient gender at baseline, various safety and adverse events).

To minimize the potential confounding effects of gender and MOCA score on the treatment effect, we will use stratified block randomization when assigning patient to one of the four study groups. The stratification factors will be gender (male/female) and MOCA score (low <22/30 and high>23/30). We will use block size of four.

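### A published fixed block of four, with a 20 IU arm recognisable by its one-nostril dosing, could let staff know the next patient's 20 IU status before randomisation for about 38% of assignments

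*Combined protocol and SAP*

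**What the plan says.** - **Randomisation (section 12.1).** Patients are allocated to the four arms in blocks, within strata formed by sex and a low or high MoCA score. On the blocks themselves the section has one sentence: "We will use block size of four". No other size is given, and nothing in the readable text keeps the size from staff who enrol patients.
- **Regimens (section 5, Table 2).** The lowest dose is "20 IU/IN (10 IU, one nostril, twice daily"); the next is "40 IU/IN (10 IU, each nostril, twice daily"). The 80 IU and placebo arms also use each nostril. The readable text describes neither a sham dose to the second nostril nor a one-nostril placebo. Planned arm sizes are 7, 7, 9 and 7.
- **Visit 2 (section 7.1.2).** Eligibility is reviewed again, the patient is randomised, and staff are to "Administer first intranasal dose in clinic and provide study kit". Section 7.3.6 adds finger sticks about 15 and 30 minutes after that dose.
- **Discretion.** Exclusion 9 in section 6.1.2 reads "Screening laboratory results that are medically relevant, in which inclusion would pose a safety risk to the subject as determined by investigator". Items 3, 5 and 6 also rest on the investigator's judgement, and section 9.2 allows further discretion. Section 7.1.1 says "Visit 2 will be scheduled within 2 weeks", with a tolerance of 5 days either way.
- **Blinding.** The summary calls the trial double blind. Section 13.6 keeps study staff blinded to individual assignments until database lock. Section 8.3 gives the product indicator to unblinded staff.

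**The concern.** A block of four that contains all four arms must hold each arm once. If one arm can be recognised when it is dosed, past assignments reveal future ones. Once a 20 IU patient has appeared in a block, nobody else in that block can be 20 IU. If three patients pass without one, the fourth must be 20 IU. Keeping the list with unblinded staff does not prevent this, because the prediction comes from doses already seen and not from the list.

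At stake is the comparability of the 20 IU arm with the others. The primary aim compares safety and tolerability descriptively by dose group, and the 20 IU arm has 7 participants, so one patient is one-seventh of it. If a clinician's view of frailty or hypoglycaemia risk affected who was randomised when a slot was known, the planned analysis could not correct for it: no covariate adjustment is planned, and such judgements may go unrecorded.

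**Working it through.** The plan states no predictability figure and no power calculation, so there is no figure of its own to reproduce.

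**Inputs.** Block size 4, four arms, strata 2 × 2 = 4 (section 12.1); 20 IU recognisable by nostril count (Table 2); N = 30. *Assumptions:* one slot per arm in each block; an observer who learns 20 IU or not 20 IU after each first dose and tracks it by stratum.

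**Step 1: one complete block.** The 20 IU slot is equally likely to be in position 1, 2, 3 or 4.

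| 20 IU in position | Later slots known to be not 20 IU | Slots known to be 20 IU | Total known beforehand |
|---|---|---|---|
| 1 | 3 | 0 | 3 |
| 2 | 2 | 0 | 2 |
| 3 | 1 | 0 | 1 |
| 4 | 0 | 1 | 1 |

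Status known: (3 + 2 + 1 + 1)/(4 × 4) = 7/16 = 43.75%.
Known not 20 IU: 6/16 = 37.5%. Known to be 20 IU: 1/16 = 6.25%.

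**Step 2: best guess in a complete block.** The chance of a correct guess is:
- position 1: 3/4
- position 2: 1/4 + (3/4)(2/3) = 3/4
- position 3: 1/2 + (1/2)(1/2) = 3/4
- position 4: 1

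Mean: (3 × 0.75 + 1)/4 = 81.25%. Always guessing not 20 IU is right 75% of the time, so the gain is 6.25 points.

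**Step 3: 30 participants in four strata, incomplete blocks included (simulation).** About 38% of assignments are certain (5th to 95th percentile about 27% to 50%), with equal or unequal strata. About 33% are certain not 20 IU and about 5% certain 20 IU; the latter is 0.05 × 30 = 1.5 patients. Best-guess accuracy is about 80%.

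**Step 4: sensitivity to 7/7/9/7.** Equal blocks do not lead to this split: 30/4 = 7.5 blocks, and it arose in about 3% of simulated four-stratum trials. Read as seven full blocks plus two extra 80 IU slots, certainty is at least 7 × 1.75/30 = 12.25/30 = 40.8%.

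**Step 5: effect of varying block size.** Same simulation with sizes 4 and 8 drawn at random, against an observer who knows the two possible sizes but not the sequence:

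| | Fixed 4 | Random 4 and 8 |
|---|---|---|
| 20 IU status certain | about 38% | about 7% |
| Best guess correct (baseline 75%) | about 80% | about 78% |
| 20 IU less than 10% likely | about 33% | about 34% |
| Mean gap, largest to smallest arm | about 1.7 | about 2.2 |

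**The case against.** **The percentage sounds worse than it is.** This stands. Most of the certainty is that the next patient is not 20 IU, already 75% likely, and nostril count says nothing about whether that patient gets 40 IU, 80 IU or placebo.

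**Varying the block size treats a symptom.** This largely stands. The root is that one arm is recognisable; if it were not, this route would give nothing away. Against an observer who knows the possible sizes, the change removes most of the certainty but little of the probabilistic advantage.

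**The chain to bias is not documented.** This stands as a limit. A reader might infer that site staff do see and track every first dose. The documents do not say who gives or attends it, and sections 5.2 and 5.3, on administration and dose loading, are redacted and may describe masking. Nothing in the readable text rules out such tracking either.

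**The opportunity to act is narrow.** This stands in part. A reader might infer that the foreknowledge operates before the patient joins the study. Consent is at Visit 1, so it can operate only before randomisation at Visit 2. Much of the information behind the discretionary exclusions is collected at Visit 1, but criteria are reviewed again at Visit 2. Moving a Visit 2 date changes an assignment only if another patient in the same stratum is randomised in between, and no accrual rate is given to show how often that could happen.

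**The trial is exploratory and unpowered.** True (sections 12.1 and 12.4). That limits the consequence, but a descriptive comparison of groups still depends on how the groups were formed.

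**Conclusion.** The vulnerability holds in limited form. Following section 12.1 and Table 2 as printed, an observer of earlier first doses would know the next patient's 20 IU status before randomisation for about 38% of assignments (43.75% in a complete block). Certainty that the patient is 20 IU covers about 5% to 6%, and best-guess accuracy is about 80% against 75%.

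This rests on one slot per arm in each block, on the one-nostril regimen being visible, and on word of first doses reaching those who judge eligibility or schedule Visit 2. The first is the natural reading; the other two are neither confirmed nor excluded by the readable text.

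A reader might go further and conclude that one or two steered patients would change the trial's result. Nothing in the documents supports that: no steering is shown, and no effect on the outcome can be calculated from what they give. The point is a cheap improvement to allocation concealment, not a finding of bias.

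**What to change.** In section 12.1, replace the block-size sentence with wording such as: *Block sizes will vary at random. They are specified only in a randomisation document held by unblinded staff and are not disclosed to staff who enrol, schedule or assess participants.* Add that Visit 2 eligibility is signed off before the assignment is requested.

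First reconcile the allocation ratio with the planned 7/7/9/7, then choose sizes that fit it. Sizes 4 and 8 suit equal allocation only.

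The cost is a short text change and a regenerated list, with no extra patients. Balance loosens slightly: in the equal-allocation simulation, the mean arm-size gap goes from about 1.7 to about 2.2 participants. The change reduces predictability but does not remove it.

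Separately, the one-nostril regimen in Table 2 and the double-blind statement must be reconciled, since that is where the recognisability comes from.

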12.2 Statistical Analysis of Primary Aim – safety, tolerability and adverse events

To assess safety and tolerability of the study drug at varying dose levels, AEs and SAEs will be categorized and summarized by study group. We will descriptively note if any group was more likely to have experienced a particular AE/SAE or generally experienced more AEs/SAEs throughout the course of the study; if we notice a significant ‘spike’ associated with a particular dosing group for a certain event, we’ll construct a chi-square test to see if it’s statistically significant. We will also assess the number of and reason for early withdrawals in each study group.

We will also monitor two key safety measures: 1) a fasting glucose < 70 mg/dL and 2) an unintended weight loss of >5% (relative to the patient’s weight at visit 2). The number of participants in each group who experience either or both of these events will be counted and descriptively compared. We will then compare the change in fasting glucose and weight at Visit 2 (Baseline/Initial Treatment) and Visit 3 (Final Treatment/Safety). In the event of an early withdrawal, measures taken at the early withdrawal visit will be used in place of Visit 3 data. We will descriptively note if any dosing group was more inclined to experience one or both of these safety events. In a similar fashion, if we notice a significant ‘spike’ associated with a particular dosing group, we’ll construct a chi-square test to see if it is statistically significant.

Secondarily, we will report the incidence of mild, moderate, and severe hypoglycemia overall and by group. Mild hypoglycemia will be defined as $54 \text{ mg/dL} \leq \text{fasting glucose} < 70 \text{ mg/dL}$; moderate hypoglycemia is $40 \text{ mg/dL} \leq \text{fasting glucose} < 54 \text{ mg/dL}$; and severe hypoglycemia is $\text{fasting glucose} < 40 \text{ mg/dL}$.

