4.1 Primary Endpoints

- Composite safety event of either: a reduction of fasting glucose to <70 mg/dL or an unintended reduction of weight >5%
- Pre-post change in safety measures (fasting glucose and weight)
- Number of AEs and SAEs

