12.3 Statistical Analysis of Second Aim – efficacy measures

For each of the efficacy outcome measures, we will report mean differences and 95% confidence intervals between Visit 2 (Baseline/Initial Treatment) and Visit 3 (Final Treatment/Safety) for each study group. In the event of an early withdrawal, measures taken at the early withdrawal visit will be used in

place of Visit 3 data, if possible. Possible trends in cognitive function, motor function, and mood and apathy scores will be addressed.

We will look at the individual components and domains assessed by the chosen cognitive, motor, mood, and apathy measures to determine if any appear to be more sensitive to IN insulin. We will also explore the data for components that have a larger dose response. That is, they increase or decrease as the dose-level increases.

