12.4 Statistical Power

As stated above, due to the sample size limitation of this study, no particular statistical power is under consideration during the study design phase with the intent to detect a meaningful clinically significant difference between study groups for any of the primary or secondary outcome measures; statistical analysis of this study will be mainly exploratory and descriptive.

The overall goal of the study is to identify a safe dose intranasal insulin with trends towards the secondary outcomes. Three different doses (and placebo) will be used, with the highest number of subjects (9) in the group with the highest dose, a model previously used by Finger et al. (2014).

13 Study Conduct Considerations

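### Section 12.2 tests a safety event only after an undefined spike is noticed, fixes no comparator or alpha, and plans no interval for any event proportion in arms of 7 to 9.

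*Combined protocol and SAP*

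**What the plan says.** Section 12.2 summarises AEs and SAEs by study group and then adds a conditional test: "if we notice a significant ‘spike’ associated with a particular dosing group for a certain event, we’ll construct a chi-square test". For fasting glucose below 70 mg/dL and unintended weight loss above 5%, it states that "The number of participants in each group who experience either or both of these events will be counted and descriptively compared", and then applies the same trigger: "In a similar fashion, if we notice a significant ‘spike’ associated with a particular dosing group, we’ll construct a chi-square test". These two events make up the composite that section 4.1 lists first among the primary endpoints.

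Section 12.1 has a general rule that "contingency tables and chi-square tests are used to compare the difference of a categorical variable", with safety and adverse events among its examples. That rule has no trigger, and it names neither a contrast nor an alpha.

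The only confidence intervals in the plan are in section 12.3, for efficacy outcomes: "we will report mean differences and 95% confidence intervals between Visit 2" and Visit 3. Section 12.4 disclaims power, calls the analysis mainly exploratory, and sets the aim: "The overall goal of the study is to identify a safe dose intranasal insulin with trends towards the secondary outcomes".

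**The concern.** Three choices are left until the data have been seen: which event to test, which group counts as having the spike, and what that group is compared with. The test is then run on the same counts that prompted it. Its p-value does not have its nominal meaning, and two analysts following section 12.2 could report opposite verdicts on identical data. The chi-square approximation is also poor at these arm sizes.

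The primary safety proportions carry no measure of precision, while the secondary efficacy means do. A group with no events would be reported as a bare zero. In a study meant to identify a safe dose, that invites the reading that the dose is safe, without showing which event rates the data rule out.

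**Working it through.** **Inputs.** Arm sizes are 7 (20 IU), 7 (40 IU), 9 (80 IU) and 7 (placebo), from Table 2; they sum to 30, with 23 on insulin. Alpha is not stated, so two-sided 0.05 is assumed. Event rates are not stated, so common rates of 2%, 10% and 20% are assumed. The plan gives no figure of its own to reproduce.

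**1. Expected counts.** The smallest expected count is largest when half the participants in the table have the event.
- Four groups, or an arm of 7 v the rest: 7 × 15/30 = 3.5.
- 80 IU v placebo: 7 × 8/16 = 3.5. An arm of 7 v placebo: 7 × 7/14 = 3.5.
- 80 IU v the rest: 9 × 15/30 = 4.5.

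Every table the rule could produce therefore has an expected count below 5.

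**2. The comparator decides the verdict.** Take events at 80 IU only. For a 2×2 table, the uncorrected statistic is N(ad − bc)² / (product of the four margins).
- 3/9 v 0/21: 30 × 63² / (9 × 21 × 3 × 27) = 7.78 on 1 df. With zeros in all other arms, the four-group statistic is also 7.78, on 3 df.
- 3/9 v 0/7: 16 × 21² / (9 × 7 × 3 × 13) = 2.87 on 1 df.
- 2/9 v 0/21: 30 × 42² / (9 × 21 × 2 × 28) = 5.00. 2/9 v 0/7: 16 × 14² / (9 × 7 × 2 × 14) = 1.78.
- Exact, 3/9: v rest 84/4060 = 0.021; four groups (Fisher-Freeman-Halton) (84 + 3 × 35)/4060 = 0.047; v placebo (84 + 35)/560 = 0.21.
- Exact, 2/9: v rest 36/435 = 0.083; four groups (36 + 3 × 21)/435 = 0.23; v placebo (36 + 21)/120 = 0.475.

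| Events at 80 IU, none elsewhere | Test | v rest | four groups | v placebo |
|---|---|---|---|---|
| 3/9 | chi-square | 0.005 | 0.051 | 0.090 |
| 3/9 | exact | 0.021 | 0.047 | 0.21 |
| 2/9 | chi-square | 0.025 | 0.17 | 0.18 |
| 2/9 | exact | 0.083 | 0.23 | 0.475 |

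With 2/9, the change of verdict comes from using chi-square in small cells. With 3/9, it remains under exact tests.

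**3. False-signal rate per event type.** All 8 × 8 × 10 × 8 = 5,120 outcomes were enumerated under a common event rate, using uncorrected chi-square at 0.05.

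| Contrast | 2% rate | 10% rate | 20% rate |
|---|---|---|---|
| Highest insulin arm v placebo | <0.01% | 0.7% | 3.5% |
| Four groups | 0.05% | 1.5% | 3.7% |
| Highest arm v rest, every such table called a spike | 2.4% | 12.2% | 14.2% |
| The same, tables with only two events in the trial not called spikes | 0.14% | 7.0% | 13.5% |
| Any insulin arm v rest, placebo spikes not counted | 1.9% | 9.5% | 10.7% |

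The third row is an upper bound. It counts placebo as a possible spike group, because Table 2 labels placebo Dose Group 4.

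**4. What zero events shows.** The two-sided 95% upper limit is 1 − 0.025^(1/n): 41% for n = 7, 34% for n = 9 and 15% for n = 23. The one-sided limit, 1 − 0.05^(1/n), is 35%, 28% and 12%. For 2/9 the Clopper-Pearson 95% interval is 2.8% to 60.0%.

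**The case against.** The strongest reply is that the study is openly exploratory. Sections 12.1 and 12.4 say so and disclaim power, the main safety summary is counts by group, and the chi-square test is only a follow-up. No confirmatory error rate is breached, and stopping rests on SAE rates under a DSMB charter (section 13.2), not on this p-value. That stands, and it limits the severity. It does not rescue the p-value, because section 12.2 runs the test expressly to judge statistical significance.

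A second reply is that section 12.1, together with summaries by study group, points to the four-group table as the default, and that this test is not inflated (1.5% at a 10% rate). One arm against all others is never mentioned and produces all the inflation at the rates shown. This is partly right, but the trigger in 12.2 refers to a particular dosing group, and nothing excludes that contrast. Section 12.1 also has no trigger, so the two sections disagree on when a test is run.

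Third, the 12.2% and 14.2% figures count placebo spikes and use uncorrected chi-square. With insulin arms only they are 9.5% and 10.7%. With Fisher's test, placebo included, they are 7.2% and 7.6%. These reductions are correct; the figures still exceed 5%.

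Last, readers could compute intervals from the published counts. They could, but the plan's own safety statement would still be made without them.

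**Conclusion.** The concern holds. Following section 12.2 can give a p-value on a primary endpoint whose verdict turns on a comparator chosen after looking: with 3/9 events at 80 IU and none elsewhere, from 0.005 to 0.090 by chi-square and from 0.021 to 0.21 by exact tests. A single four-group test is not inflated; the fault is the free choice of event, group and contrast. The error rates rest on the assumed alpha of 0.05, the assumed common event rates and, at their upper end, on every qualifying table being called a spike. The missing intervals need no such assumption: zero events in an arm leaves true rates up to 41% (n = 7) or 34% (n = 9) compatible with the data.

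The plan should be changed on this point. The damage is confined to how the safety result is read, since no stopping or dose-selection rule in the documents uses the p-value.

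**What to change.** Amend section 12.2 before unblinding:

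1. Always report exact (Clopper-Pearson) 95% intervals for the composite, hypoglycaemia, SAEs and early withdrawals, by group and for pooled insulin (n = 23). The pooled interval averages over three doses and does not establish the safety of any one of them.
2. Report adverse event categories picked out by a spike descriptively, with no p-value.
3. If a test of the composite is kept, name one exact test with its contrast and alpha, and run it whether or not a spike is seen. Align section 12.1 with this.
4. Word the safety conclusion by the rate the interval excludes, for example: no events in 7, rates above 41% excluded (two-sided 95%).

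The cost is SAP wording and trivial analysis work. The intervals will be wide. Any retained test will have low power: an exact four-group test at 0.05 has 23% power for 30% v 5% elsewhere if the 80 IU arm is raised, and 19% if an arm of 7 is raised (58% and 54% for 50% v 5%). It also ignores dose order.
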